### **9.2. Statistical and Analytical Plans**

Intention-to-treat analysis will be carried out; proportions will be evaluated using chi-square tests, non-parametric variables with Mann-Whitney *U* and parametric variables with Student's *t* tests as appropriate.

An interim analysis will be done when 50% of recruitment has been reached to check for incidence of adverse outcomes such as 30-day or 60-day MACE. If there is a significant increase in 30-day or 60-day MACE in the intervention arm as compared to the control arm, the study will be stopped.

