### **c. Rationale for Study Design**

This is a randomized controlled trial where subjects will be stratified by gender and then randomized 1:1 to either the control or the intervention arm. This is because gender may affect the cardiovascular risk significantly and hence affect the outcome of MACE.

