### **2.2. Primary Objectives**

1. We aim to evaluate if shared decision-making with patients using the Chest Pain Choice (CPC), a visual decision aid tool, will reduce admissions to the ED observation unit among patients with low-risk chest pain at the index visit to the emergency department.

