## **6.1. Randomisation and Blinding**

Subjects will be stratified by gender and then randomized 1:1 to either the control arm or the intervention arm by the means of a computer program. Allocation will be done after recruitment via the means of sealed, opaque envelopes. The primary physician, study team and patient will not be blinded, as blinding is not possible. However, as the outcomes are objective, the risk of bias is minimal.

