## **9. SAMPLE SIZE AND STATISTICAL METHODS**

### **9.1. Determination of Sample Size**

A sample size of 164 patients (82 in each arm) will provide 80% power to detect an absolute difference of 20% reduction in admissions to ED observation unit in the intervention arm between the 2 groups, with 2-sided alpha of 0.05.

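### Randomisation is stratified by gender, but the chi-square test planned for observation-unit admission ignores gender and may give up some precision

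*Combined protocol and SAP*

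**What the plan says.** Section 6.1 states: "Subjects will be stratified by gender and then randomized 1:1 to either the control arm or the intervention arm". Sections 1.2 c, 5, 5.1, 6 and 6.2 b say the same. The reason is given in section 1.2 c: "This is because gender may affect the cardiovascular risk significantly and hence affect the outcome of MACE". Section 5.1 repeats it. No section links gender to admission.

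The primary objective (section 2.2) is to find out whether the decision aid "will reduce admissions to the ED observation unit among patients with low-risk chest pain at the index visit to the emergency department". That outcome is binary.

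Section 9.2 is the whole analysis plan: "Intention-to-treat analysis will be carried out; proportions will be evaluated using chi-square tests", with Mann-Whitney U and Student's t tests for other variables. It describes no stratified or adjusted analysis and no confidence interval.

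Section 9.1 gives the size: "A sample size of 164 patients (82 in each arm) will provide 80% power". The target is a 20-point absolute reduction at two-sided 0.05, and no control admission rate is given. Section 3.1 plans to enrol 200.

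**The concern.** An analysis would normally use the factors by which randomisation was stratified. When the arms hold the same mix of men and women by design, a gender difference in admission cannot contribute to the difference between arms. The pooled chi-square nevertheless counts that variation in its standard error. The standard error is then too large, the actual type I error falls below 5%, and power is lost.

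Without such balance, gender adds real noise to the arm difference. The chi-square allows for that noise correctly on average, but a stratified test would remove it. In both cases the trial has set up the strata and then does not use them for its primary outcome.

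**Working it through.** **Inputs from the documents.** 82 per arm, 20-point absolute reduction, two-sided alpha 0.05, 80% power (section 9.1); 1:1 allocation stratified by gender (section 6.1); binary primary outcome (section 2.2).

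**Assumptions, because the documents give no figure.** Control admission rate 40%; equal numbers of men and women; a male-female gap g in admission risk of 0 to 40 points; the same 20-point reduction in each gender.

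**Step 1: the plan's own figure.** The pooled formula without continuity correction is n = [1.96·√(2p̄(1−p̄)) + 0.8416·√V]² / 0.20², with V = pc(1−pc) + pt(1−pt). For 40% v 20%, p̄ = 0.30 and V = 0.24 + 0.16 = 0.40. Then n = (1.270 + 0.532)² / 0.04 ≈ 81.2, or 82 per arm, with power 80.4%. The symmetric pair 80% v 60% gives the same. So 164 is attainable at these rates, but cannot be confirmed without a stated control rate.

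**Step 2: how much a gender gap widens the unstratified interval.** With half men and half women, the average within-gender variance in one arm is p(1−p) − g²/4. Over two arms the stratified variance term is V − g²/2. The ratio of unstratified to stratified standard error is √[V / (V − g²/2)]:
- g = 0.10: √(0.40/0.395) = 1.006
- g = 0.20: √(0.40/0.380) = 1.026
- g = 0.30: √(0.40/0.355) = 1.061
- g = 0.40: √(0.40/0.320) = 1.118

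At g = 0.20, a male share of 60% or 70% changes the ratio only to 1.025 or 1.022.

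**Step 3: type I error with balance within gender.** Under the null at 30% in both arms, V = 0.42. The chi-square in effect uses the critical value 1.96·√[0.42/(0.42 − g²/2)]. For g = 0.20, 0.30 and 0.40 this is about 2.01, 2.07 and 2.18, so the two-sided error is about 4.5%, 3.8% and 2.9%. Simulation agrees: 4.4%, 3.8% and 3.0%, against about 4.9% for CMH.

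**Step 4: power with balance within gender (simulated, 82 per arm, 40% v 20%).**

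| Gender gap | Chi-square | CMH | Gain |
|---|---|---|---|
| 10 points | 80.9% | 81.2% | 0.3 |
| 20 points | 81.5% | 82.8% | 1.3 |
| 30 points | 82.1% | 85.2% | 3.1 |
| 40 points | 83.4% | 88.8% | 5.4 |

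The 40-point row is extreme: it means 60% v 40% in one gender and 20% v 0% in the other. If the aid instead halves admission in each gender, the gains are smaller. At 20/30/40 points, power rises from 81.2 to 81.9%, 81.8 to 83.3% and 82.0 to 85.0%.

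**Step 5: unrestricted randomisation within gender (simulated, 164 in total).** The chi-square's type I error is 5.0 to 5.1% at every gap. At 20/30/40 points its power is 80.6% throughout, against 82.2/84.8/88.5% for CMH. The 5% is an average over allocations. In the roughly 19% of trials where the male share differs by 10 points or more between arms, the chi-square's error is about 6%, 8% and 10% at those gaps, while CMH stays near 5%.

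**Step 6: cost when gender does not predict admission.** CMH loses at most about 0.4 points of power.

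**The case against.** The strongest reply is that the loss is conditional and usually small. Three parts of it stand.

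- The documents tie gender to cardiovascular risk and MACE, never to admission. Eligibility narrows the population to HEART 0-3 with a normal troponin and a non-ischaemic ECG (sections 3.3 and 3.4). Gender is not among the HEART components listed in the rationale for the study population. Section 6 puts variation in usual care down to factors such as social set-up and availability of testing. Against this, section 1.2 a attributes testing of low-risk patients partly to clinicians' very low threshold of acceptable risk, so a gender gap is plausible, but its size is unknown.
- No block size or other restriction within gender is stated. Sections 6 and 6.1 mention only an online generator or computer program, with sealed envelopes. A reader might infer from the word stratified that the arms are balanced within gender and that the test's true error must be below 5%. The documents do not support that as fact: without restriction the chi-square keeps 5%.
- At 40% v 20% the chi-square stays above 80% power at every gap. With 100 per arm, as the 200 in section 3.1 would allow, and a 20-point gap, its power is about 88% and the gain is under one point.

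This limits the size of the point but does not remove it. CMH holds its size under either randomisation scheme, gains power whenever gender predicts admission appreciably, and costs almost nothing otherwise.

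**Conclusion.** The mismatch between stratified randomisation and unstratified primary analysis is certain. Its consequence is conditional. If admission differs by gender and the arms are balanced within gender, the chi-square is conservative. If randomisation within gender is unrestricted, it is correctly sized on average but less precise than it could be. Under the stated assumptions the cost is 0.3 to 1.3 points of power for gaps of 10 to 20 points and 3.1 to 5.4 points for gaps of 30 to 40.

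Two stronger readings should be resisted. One is that the primary result's standard errors are definitely too wide, or that the test is invalid. Neither follows, since both conditions are undocumented and false positives are not inflated overall. The other is that the t and Mann-Whitney tests share the fault for the primary outcome. They do not bear on it, because admission is binary, and the calculations here say nothing about the scale scores.

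This is an efficiency and consistency point worth making because the remedy is nearly free. The missing control admission rate in section 9.1 is a separate and larger gap.

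**What to change.** In section 9.2, make the primary analysis of observation-unit admission a Cochran-Mantel-Haenszel test stratified by gender, at two-sided 0.05. Report the Mantel-Haenszel risk difference with its 95% CI, and keep the unstratified chi-square as a sensitivity analysis. Specify this before outcome data are seen, so that the choice to adjust cannot appear to depend on the result.

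It would also help to state in section 6.1 how allocation is restricted within gender, although the recommendation holds either way.

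The cost is a sentence or two of wording, with no new data and no more patients. The only statistical downside is the loss in step 6 if gender turns out not to predict admission.

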## **2. HYPOTHESIS AND OBJECTIVES**

### **2.1. Hypothesis**

Incorporating the Chest Pain Choice visual aid in shared decision making can help to decrease unnecessary admissions for patients with low risk chest pain to the observation ward, as well as increase patient knowledge with regards to their own condition.

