### **2.3. Secondary Objectives**

1. To determine if the CPC can improve patient knowledge and increase patient involvement in shared decision-making
2. To evaluate the impact on the incidence of MACE, ED re-attendances and downstream cardiac evaluation (either stress tests or computed tomography of the coronary arteries) at 30-days and 60-days with the implementation of CPC

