## **6. METHODS AND ASSESSMENTS**

This is a randomized controlled trial; involving patients aged 21 years and above with low risk chest pain. Patients enrolled will be stratified by gender and then randomized 1:1 into either the intervention arm (CPC) or control arm (usual care). Randomization will be done via an online randomization generator. Recruitment will take place from Sunday 0800 hours to Thursday 2359 hours as inpatient cardiac evaluation investigations such as stress tests and CTCA are only available during weekdays, hence limiting the utility of the ED observation unit on weekends. Those under the intervention arm will receive the Chest Pain Choice visual aid prior to discussion with their primary physician regarding disposition. Data will be collected regarding the patients' age, demographics, past medical history and co-morbidities, cardiovascular risk factors, current medications, variables regarding their current visit such as vital signs, symptoms, laboratory results and electrocardiogram results, treatment received at the emergency department, eventual disposition and downstream cardiac test results if any. In addition to this, patients will answer a questionnaire which will assess patient knowledge, perceptions regarding the information received during consultation, patient satisfaction, as well as the Trust in Physician scale (a tool that assesses interpersonal trust in a patient-physician relationship) and the Decisional Conflict scale (an established tool that assesses personal perceptions regarding decision-making). Please see the data collection form and the patients' questionnaires in Appendix 2.

After discussion between the patient and his/her attending physician, patients will either be discharged from the emergency department with or without outpatient tests to evaluate their cardiac function (e.g. stress tests, CTCA) and/or outpatient Cardiology appointment or admitted to the ED observation unit for further observation and serial troponin testing, whereby further investigations for cardiac evaluation (e.g. stress tests, CTCA) may or may not be done or planned, at the discretion of the attending physician. There is variability in what is considered standard care, as it is dependent on several factors such as the patient's social set-up, availability of inpatient cardiac evaluation, etc., and hence standard care will not be strictly defined.

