The patients in both groups will be assessed regarding their pre- and post-consultation knowledge as well as satisfaction during this visit by standardized questionnaires. The patients will be followed up at 60 days to find out if they had MACE, ED re-attendances, as well as whether further tests for cardiac evaluation were done. This will be done via a review of their electronic medical records or via telephone contact if electronic medical records are not available. A MACE is defined as all-cause mortality, myocardial infarction or coronary revascularisation.

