### *b. Study Visits and Procedures*

Patients enrolled will be stratified by gender and randomized 1:1 into either the intervention arm (CPC) or control arm (usual care). For patients with low risk chest pain, an initial electrocardiogram and serial troponin will be done as part of standard care. Serial serum troponin tests will also be taken at the discretion of the attending physician. Further tests to evaluate the patient's cardiac function such as stress tests (e.g. stress treadmill electrocardiogram, stress myocardial perfusion imaging, etc.) or a computed tomography of the coronary arteries (CTCA) may either be arranged as part of the patient's ED observation unit stay or outpatient as part of standard care. For research purposes, those under the intervention arm will receive the chest pain choice visual aid prior to discussion with their primary physician regarding disposition.

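### Section 9.2 leaves the knowledge comparison undefined and does not use the pre-consultation score already collected; ANCOVA on that score would be a free gain for this secondary outcome

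*Combined protocol and SAP*

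**What the plan says.** The hypothesis (section 2.1) is that the aid will cut admissions, "as well as increase patient knowledge with regards to their own condition". The primary objective (section 2.2) concerns admissions only: whether use of the aid "will reduce admissions to the ED observation unit among patients with low-risk chest pain at the index visit". Knowledge comes first among the secondary objectives (section 2.3): "To determine if the CPC can improve patient knowledge and increase patient involvement in shared decision-making".

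On measurement, section 6 states that "patients will answer a questionnaire which will assess patient knowledge, perceptions regarding the information received during consultation", and further on that "The patients in both groups will be assessed regarding their pre- and post-consultation knowledge".

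On timing, section 6.2.b says that "those under the intervention arm will receive the chest pain choice visual aid prior to discussion with their primary physician", and section 6.1 that "Allocation will be done after recruitment via the means of sealed, opaque envelopes". Neither section places the first knowledge questionnaire relative to the envelope or the aid.

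On analysis, the whole text on between-arm tests is one sentence in section 9.2: "proportions will be evaluated using chi-square tests, non-parametric variables with Mann-Whitney" U, and Student's t for parametric variables, as appropriate. It names no knowledge variable, covariate or model. Appendix 2 holds the data collection form and questionnaires. It is not available here, and it is not described as an analysis plan.

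**The concern.** Two things are missing for an outcome that the hypothesis names.

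First, the compared quantity is undefined. With a score before and after, the listed tests could be applied to the post score or to the change. These are different tests with different power, and the text leaves the choice until after the data are seen.

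Second, none of the three listed tests can take a covariate. A pre-consultation score is collected from every patient and then not used in the way that would sharpen the comparison. At stake is the precision of the knowledge result, not its validity.

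Adjustment is sound only if the pre-score is a true baseline. The aid is handed over before the discussion with the physician, so a questionnaire completed just before that discussion could fall on either side of the aid. Adjusting for, or subtracting, a score taken after the aid would remove part of the effect being measured.

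**Working it through.** **The plan's own figure.** Section 9.1 gives 82 per arm for a 20-point reduction in admissions, 80% power, two-sided 0.05. The control rate is not stated. If 40% v 20% is assumed, the pooled formula gives

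[1.960·√(2·0.3·0.7) + 0.842·√(0.4·0.6 + 0.2·0.8)]² / 0.2² = 81.2, so 82.

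This sizes admissions only. No figure is given for knowledge.

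**Inputs for knowledge.** From the documents: 82 per arm (section 9.1), 200 enrolled and so 100 per arm at 1:1 (section 3.1), two-sided 0.05. Assumed: equal SDs before and after, pre/post correlation r from 0 to 0.7, and an effect set so that the post-score test has 80% power with 82 per arm:

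d = (1.960 + 0.842)·√(2/82) = 0.4375 SD.

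**Variance relative to the post score.** Post score: 1. Change: 2(1−r). ANCOVA: 1−r². ANCOVA is never above 1. Its ratio to change is (1−r²)/[2(1−r)] = (1+r)/2, which is never above 1 either.

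**Power** = Φ(d/√(2v/n) − 1.960), where v is the relative variance. For example, at n = 82 and r = 0.5 for ANCOVA, v = 0.75, so 2.802/√0.75 − 1.960 = 1.275 and the power is 90%.

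| r | v, change | v, ANCOVA | Post, 82 per arm | Change, 82 | ANCOVA, 82 | Post, 100 per arm | ANCOVA, 100 |
|---|---|---|---|---|---|---|---|
| 0 | 2.0 | 1.00 | 80% | 51% | 80% | 87% | 87% |
| 0.2 | 1.6 | 0.96 | 80% | 60% | 82% | 87% | 88% |
| 0.3 | 1.4 | 0.91 | 80% | 66% | 84% | 87% | 90% |
| 0.5 | 1.0 | 0.75 | 80% | 80% | 90% | 87% | 95% |
| 0.7 | 0.6 | 0.51 | 80% | 95% | 97.5% | 87% | 99% |

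**Shape of the score.** The scale is not visible, so two shapes were simulated (82 per arm, 20,000 trials per setting, same effect on a latent normal scale, latent r = 0.3 / 0.5 / 0.7, gender not modelled).

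- Score bounded at 0–8, with 16% of controls at the ceiling: Mann-Whitney on the post score 75 / 76 / 76%, ANCOVA 79 / 86 / 95%.
- Strongly skewed (lognormal) score: Mann-Whitney 78 / 77 / 78%, ANCOVA 69 / 75 / 87%, rank-based ANCOVA 81 / 87 / 96%.

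Type I error was 4.6–5.3% for all tests. So a bounded score does not undermine ordinary ANCOVA. A strongly skewed one costs it power against a rank test at r = 0.3 and 0.5.

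**The open choice.** If both the post score and the change were tested and the better one reported, simulation puts the two-sided false-positive rate at 8.8 / 9.1 / 9.3% at r = 0.3 / 0.5 / 0.7.

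**The case against.** The planned tests are valid under randomisation, knowledge is secondary, and the plan sets no power target for it. On that view, asking for a covariate is a preference for a better method and not the correction of an error. This stands, and it limits the point to an improvement.

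The size rests wholly on assumed inputs, and the effect was chosen to give 80%. This also stands. At r = 0 to 0.2 the gain over the post score is only 0 to 1.6 points. At the planned 100 per arm it is 3 / 7.5 / 12 points at r = 0.3 / 0.5 / 0.7, against 4 / 10 / 17.5 with 82. Over the change score at r = 0.7 and 82 per arm it is about 2.5 points.

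Appendix 2 may already fix the order of questionnaire and aid. That is possible, and the proposed sentence on order is conditional on it. It would not settle which quantity is compared.

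Three stronger readings are tempting, and the documents do not support them. A reader might infer that the knowledge result would be biased. An unadjusted comparison of post scores is unbiased under randomisation, and so is one of change if the first score precedes allocation. A reader might infer that the first questionnaire follows the aid. The visible text is silent, and calling the score pre-consultation in both arms fits either order. A reader might infer that the team means to test both quantities and report the better one. Nothing says so, and the 8.8–9.3% shows only what an unspecified comparison would permit.

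**Conclusion.** The point holds as a free improvement to a secondary analysis. Section 9.2 does not define the knowledge comparison and leaves a collected baseline score unused. Under equal SDs and a linear pre/post relation, ANCOVA is at least as precise as either alternative at every correlation. The power gain over the post score with 82 per arm runs from nothing at r = 0 to 17.5 points at r = 0.7. Over change it runs from 29 points down to 2.5 across the same range. The correlation is unknown, so neither end can be claimed.

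The admissions analysis and the 164 are untouched. The recommendation depends on the pre-score being taken before allocation and before the aid, which the visible text does not establish.

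**What to change.** In section 9.2, add:

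> Knowledge will be compared between arms by ANCOVA of the post-consultation score on arm, pre-consultation score and gender; the adjusted mean difference with 95% CI and its p-value is the main result for this outcome. A rank-based ANCOVA with the same covariates will be reported as a sensitivity analysis.

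In section 6.2.b, unless Appendix 2 already fixes the order, add:

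> The pre-consultation questionnaire is completed before the allocation envelope is opened and before the aid is given.

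If that order cannot be assured, compare post-consultation scores adjusted for gender only.

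The rank analysis is better as a fixed sensitivity analysis than as a replacement triggered by the look of the data. A trigger without a threshold would leave a choice open again. Testing on ranks while reporting a mean difference gave a significant rank test with an interval that included zero in about 10–16% of simulated skewed trials.

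Cost: two sentences in section 9.2, at most one in section 6.2.b, and slightly more analysis work. No new data are needed. The downside is some loss of power against a rank test if the score is strongly skewed, which the sensitivity analysis would show.

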#### **a. Rationale for the Study Purpose**

Chest pain is a common presenting complaint in the Emergency Department (ED). Cardiac testing in low-risk patients poses unnecessary costs and resource utilisation, which may in part be due to clinicians adopting a very-low-risk threshold for discharge without testing. The use of the Chest Pain Choice - a visual aid - for shared decision making, has been shown to be effective in increasing patient knowledge and decreasing the rate of admission to an observation unit for cardiac testing, among patients with chest pain who are at low risk for acute coronary syndromes. This can be adapted to our local context to decrease unnecessary admissions to the ED observation unit (referred to as the Extended Diagnostic Treatment Unit or EDTU in our institution). This study aims to assess if using a visual decision aid for shared decision making between physician and patient can safely help to decrease unnecessary admissions to the ED observation unit, as well as its impact on patient knowledge, satisfaction, as well as 30-day and 60-day Major Adverse Cardiac Events (MACE).

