#### **b. Rationale for Study Population**

The target population is that of adults aged 21 years and above who present to ED with chest pain that is considered low risk based on the HEART score (HEART score 0-3). The HEART score is a validated scoring system for patients aged 21 years and above who present with

symptoms suggestive of Acute Coronary Syndromes. The HEART score assigns different points for various features in the patient's history, ECG features, age group, presence of risk factors, and initial troponin level, in order to generate a score that corresponds to a range of percentages for the risk of 6-week MACE. Patients with a HEART score of 0-3 correspond to a 6-week MACE risk of 0.9-1.7%. Since the risk of 6-week MACE is low in these patients, outpatient follow-up and cardiac testing for underlying coronary artery disease can be considered instead of ED observation unit admission. This is also in keeping with current institutional practices.

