### **2.4. Potential Risks and benefits:**

#### **a. End Points – Efficacy**

The direct benefits among research participants who are randomized to the CPC arm are that they may have a better understanding regarding their condition and feel more empowered in making a shared decision together with their attending physician.

The indirect benefit is that implementation of the CPC may safely reduce hospital admissions in patients with low-risk chest pain.

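### About one MACE per arm is expected and section 9.2 names only chi-square for it, so a non-significant comparison cannot show that admissions fall safely

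*Combined protocol and SAP*

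**What the plan says.** Section 9.2 states that "proportions will be evaluated using chi-square tests". The same sentence ends with "parametric variables with Student's *t* tests as appropriate", which is the only qualifier on the choice of test. The section gives no exact test, confidence interval, margin or rule for sparse counts, and does not say whether a continuity correction applies.

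MACE (death from any cause, myocardial infarction or coronary revascularisation) is a secondary outcome at 30 and 60 days (section 2.3). The rationale for the study population gives the expected rate: "Patients with a HEART score of 0-3 correspond to a 6-week MACE risk of 0.9-1.7" per cent.

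The trial is sized on admissions alone. Section 9.1 says "A sample size of 164 patients (82 in each arm) will provide 80% power to detect an absolute difference of 20% reduction", "with 2-sided alpha of 0.05". Section 3.1 sets enrolment at 200, which is 100 per arm at 1:1.

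Section 1.2.a says the study will assess whether the aid "can safely help to decrease unnecessary admissions to the ED observation unit". Section 2.4.a lists as an indirect benefit that "implementation of the CPC may safely reduce hospital admissions". Section 9.2 also makes a significant rise in MACE in the intervention arm, at 50% of recruitment, a reason to stop the study.

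**The concern.** Section 2.4.b names the mechanism of possible harm: if more patients go home, further cardiac testing and definitive management may be delayed. MACE is therefore the outcome that shows whether fewer admissions are a benefit. If the only planned analysis of MACE is a significance test on about one event per arm, the expected result is no significant difference, whether or not the aid does harm. Nothing in section 9.2 tells the analyst or the reader how little such a result would mean, and no interval is planned that would show it.

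**Working it through.** **Inputs.** MACE risk 0.9% to 1.7% at 6 weeks (rationale for study population), applied to 30- and 60-day MACE because 6 weeks lies between them; this is an assumption. Per-arm size 82 (section 9.1) or 100 (section 3.1). Two-sided alpha 0.05 (section 9.1). Interim look at half of recruitment: 41 or 50 per arm (section 9.2).

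**1. The plan's own figure.** Section 9.1 does not state the control admission rate. Assuming 40% v 20%, the pooled-variance formula gives n = [1.96·√(2·0.3·0.7) + 0.8416·√(0.4·0.6 + 0.2·0.8)]² / 0.2² = (1.270 + 0.532)² / 0.04 = 81.2, so 82 per arm. An assumed 80% v 60% gives the same. The 164 is thus reproducible for admissions. No size, power or margin is given for MACE.

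**2. Expected MACE per arm** (n × risk).
- 82 per arm: 82 × 0.009 = 0.74 to 82 × 0.017 = 1.39
- 100 per arm: 0.90 to 1.70
- Interim: 41 × 0.009 = 0.37 to 50 × 0.017 = 0.85

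All are far below the customary minimum expected count of 5.

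**3. How chi-square behaves.** Enumerating both binomials under equal risk, the actual two-sided type I error of the uncorrected test is 0.6-2.6% at 82 per arm and 1.1-3.4% at 100. The approximation is poor, but the test rejects too seldom, not too often.

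**4. Power to detect harm.** Same enumeration, counting only significant results with more MACE in the CPC arm, uncorrected chi-square, over control risks of 0.9% to 1.7%:

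| True effect of CPC on MACE | 82 per arm | 100 per arm |
|---|---|---|
| Doubling | 2.9-8.3% | 4.4-9.9% |
| Tripling | 8.9-19.9% | 12.3-23.7% |
| Fivefold | 27-50% | 34-60% |

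For scale, 80% power for a doubling at two-sided 0.05 would need about 2,580 per arm from 0.9%, or 1,349 per arm from 1.7%.

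**5. What the data could exclude.** With no events in the CPC arm, the exact 95% upper limit is 1 − 0.025^(1/82) = 4.4%, or 1 − 0.025^(1/100) = 3.6%. That is between about 2 times (3.6/1.7) and 5 times (4.4/0.9) the expected risk.

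With one event in each arm, the Newcombe half-width is √[(p − l)² + (u − p)²], where l and u are the Wilson limits:
- 82 per arm: p = 1.22%, l = 0.22%, u = 6.59%, so √(1.00² + 5.37²) = 5.5 points
- 100 per arm: p = 1.00%, l = 0.18%, u = 5.45%, so √(0.82² + 4.45²) = 4.5 points

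**6. What Fisher's test would do instead.** From a control risk of 1.3% (assumed, the middle of the range), power for a tripling falls from 15% to 4% at 82 per arm and from 19% to 7% at 100. With no control events, the uncorrected chi-square is significant from 4 CPC events and Fisher's test from 6. At an interim look with 41 per arm, 4 v 0 gives p = 0.040 by uncorrected chi-square, while 5 v 0 gives p = 0.055 by Fisher's test.

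**The case against.** Several points stand on the other side.

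- A reader might infer that the chi-square test is invalid in the sense of producing false alarms. It is not: its actual error rate is below 5%. Nor does it necessarily disagree with an exact test. At 82 per arm, 4 v 0 gives p = 0.043 uncorrected, but 0.129 with a continuity correction, close to Fisher's 0.120. Section 9.2 does not say which form is meant.
- A reader might infer that the plan will treat non-significance as proof of safety. No section says so, and there is no non-inferiority claim or margin.
- A reader might infer that demonstrating safety is a formal aim. Section 1.2.a speaks only of assessing, section 2.4.a of what may happen, and the hypothesis (2.1) and primary objective (2.2) carry no safety claim. Section 2.3 seeks only to evaluate the impact on MACE, and section 2.4.b openly names higher MACE as a risk.
- Low power for a rare secondary outcome is common and is not in itself an analysis error.
- The qualifier in section 9.2 could be read as permitting an exact test for sparse counts. On that reading the test would be chosen without a stated rule, and there would still be no interval.

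These points limit the charge. They do not remove the gap between a stated purpose that includes safety and a planned MACE analysis that can say almost nothing about it.

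**Conclusion.** The point holds in limited form. With 0.7 to 1.7 expected events per arm, power of 9-24% for a tripling, and an upper limit of 3.6-4.4% even after no CPC events, a non-significant MACE comparison cannot support the purpose in section 1.2.a of assessing whether admissions fall safely. The fault lies in having no interval and no statement of what the comparison can show, rather than in an inflated error rate. Power is higher, though still at most 60%, for a fivefold rise.

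The conclusion rests on applying the protocol's 6-week risk to 30 and 60 days, and on 82 to 100 analysed patients per arm. It does not touch the primary comparison of admissions.

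**What to change.** In section 9.2, take MACE out of the general chi-square sentence and make its analysis descriptive:
- event counts per arm at 30 and 60 days;
- exact (Clopper-Pearson) 95% intervals per arm;
- a Newcombe or exact unconditional 95% interval for the risk difference;
- a statement that a non-significant difference will not be taken as evidence of safety, and that the trial is not sized to establish safety.

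Align the wording on safety in section 1.2.a with this.

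Do not simply replace chi-square with Fisher's test. It would reduce sensitivity to harm (step 6) in a test that is already conservative. Because the interim stopping rule in section 9.2 depends on a significant rise in MACE, that section should name the test, and any continuity correction, on which the rule rests. It should also disclose what a change of test does to the number of events needed to trigger the rule.

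The cost is a change of wording in the protocol and analysis plan, with no extra patients and no change to the primary analysis. The downside is that the safety conclusion becomes less favourable: the report will show wide intervals where it might have shown only a non-significant p-value.
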